9.10.3. Regulatory Reporting Requirements for SAEs

Prompt notification by the investigator to the sponsor of an SAE is essential so that legal obligations and ethical responsibilities towards the safety of participants and the safety of a study drug under clinical investigation are met.

The sponsor has a legal responsibility to notify both the local regulatory authority and other regulatory agencies about the safety of a study drug under clinical investigation. The sponsor

will comply with country-specific regulatory requirements relating to safety reporting to the regulatory authority and the investigators. The principal investigator at each site will be responsible for notifying the relevant institutional review board (IRB)/independent ethics committee (IEC) of these additional SAEs, according to local standard operating procedures.

Investigator safety reports must be prepared for suspected unexpected serious adverse reactions according to local regulatory requirements and sponsor policy and forwarded to investigators, as necessary.

An investigator who receives an investigator safety report describing an SAE or other specific safety information (eg, summary or listing of SAEs) from the sponsor will review and then file it along with the IB and will notify the IRB/IEC, if appropriate according to local requirements.

9.10.4. Pregnancy Reporting and Monitoring

Study drug will be immediately discontinued in a female participant upon confirmation of a positive pregnancy test result and will be reported to the sponsor within 24 hours of first awareness. Pregnancy in a female partner of male participant will be reported to the sponsor within 24 hours after obtaining the necessary signed ICF from the female partner. The participant/consenting pregnant female partner will be followed to determine the outcome of the pregnancy.

While pregnancy itself is not considered to be an AE or SAE, any pregnancy complication or elective termination of a pregnancy for medical reasons will be reported as an AE or SAE. Abnormal pregnancy outcomes (eg, spontaneous abortion, fetal death, stillbirth, congenital anomalies, ectopic pregnancy) are considered SAEs and will be reported as such. Elective abortions without complications should not be handled as AEs.

Any post-study pregnancy-related SAE considered reasonably related to the study drug by the investigator will be reported to the sponsor. While the investigator is not obligated to actively seek this information in former study participants or their pregnant female partners, he or she may learn of an SAE through spontaneous reporting.

9.11. Cognitive Performance Assessments

The following Cogstate AD battery of cognitive function tests will be completed digitally.

- **Detection test** (3 min; measures processing speed): A playing card is presented face down. The participant is asked to press “yes” as soon as the card flips over.
- **Identification test** (3 min; measures attention): A playing card is presented face down. When the card flips over, the participant must decide whether or not it is red. If the card is red, they press “yes” and if it is not, they press “no.” The participant works as quickly and accurately as possible.
- **One-card learning test** (6 min; measures visual memory): A playing card is presented face up. The participant must decide whether they have seen the card before in the test. Accordingly, they will press “yes” or “no” as quickly and accurately as possible.

- **One back test** (4 min; measures working memory): A playing card is presented face up. The participant must decide whether the card is the same as the previous card. If the card is the same, the participant should press “yes” and if it is not, the participant should press “no.” The participant is encouraged to work as quickly and as accurately as possible.
- **International shopping list test** (5 min; measures verbal learning): After being read a shopping list, the participant is asked to recall as many items from the list as possible.
- **International shopping list test—delayed recall** (5 min; measures verbal memory): After some time has passed, the participant is asked to recall again as many items from the shopping list as possible.
- **Continuous paired associate learning test** (7 min; measures visual memory): The participant must learn and remember the pictures hidden beneath different locations on the screen.
- **Modified Groton maze learning test** (7 min; measures executive function): A 10×10 grid of tiles is presented on the screen. A 28-step pathway is hidden among the tiles. A blue tile indicates the start. A tile with red circles indicates the finish. The participant must move 1 step at a time from the start toward the finish by touching a tile next to their current location. If the correct move is made, a green checkmark appears. If the move is incorrect, a red cross appears. Once completed, the participant is returned to the start location to repeat the test by remembering the pathway that was just completed.

The following assessments of semantic and phonemic fluency will also be completed.

- **Letter fluency** (3 min; measures verbal fluency): Using the 3-letter set of F, A, and S, the participant is given 1 minute to name as many words as possible beginning with each one of the letters in turn, for a total of 3 minutes. The score is the total number of unique correct words.
- **Category fluency** (1 min; measures verbal fluency): Using a single category of animals, the participant is given 1 minute to name as many unique words as possible within that category. The score is the total number of unique correct words.

9.12. Neurophysiological Assessments

Details of EEG procedures will be described outside of this study protocol. Because the postdose EEG assessment will be approximately 2 hours after the predose EEG assessment, the electrodes should remain in place to reduce variability and ensure consistent testing conditions.

9.12.1. Resting State qEEG (Eyes Open/Closed)

Resting state quantitative electroencephalography (qEEG) recordings will be performed with alternating periods of eyes open and eyes closed. During part of the recording session, participants will face a featureless wall and will be instructed not to stare, not to move their head and eyes, and to suppress eye blinks.

9.12.2. Auditory Oddball Assessment for Event-Related Potential (ERP)

Participants will be seated wearing the EEG cap and headphones and instructed to sit still and relax. During this task, participants will be presented with a series of auditory tones. Of these tones, the majority are presented as frequent stimuli while some are presented as deviant/infrequent stimuli. Participants will be instructed to pay attention to the tones and identify the infrequent/deviant tones.

9.13. Neuroimaging Assessments

Exploratory neuroimaging modalities will be used to measure the potential PD effects of CY6463 in the brain. Modalities include arterial spin labeling (ASL) and functional magnetic resonance imaging (fMRI).

Regional and overall changes in cerebral blood flow will be measured using ASL during resting state. Brain activity/reactivity will be measured using fMRI, a relative measure based on the blood-oxygen-dependent effect performed during resting state. MRI will also be used to detect subtle changes in brain tissue by quantitatively measuring changes in cellular microstructure and white matter structural integrity.

Details of imaging acquisition procedures will be described outside of this study protocol.

10. STATISTICAL CONSIDERATIONS

See Section 5 for a list of the study objectives and their corresponding endpoints.

10.1. Statistical Hypotheses

The primary objective of the study is to evaluate the safety and tolerability of CY6463 (15 mg QD) after 12 weeks of treatment. No formal statistical hypotheses will be conducted to assess this objective.

If appropriate, comparisons between CY6463 and placebo will be made to investigate the exploratory objectives. Such tests will be 2-sided with a 10% significance level. Due to the exploratory nature of this study, there will be no adjustment of the p-values for multiple testing. All reported p-values will be considered nominal.

10.2. Sample Size Determination

A sample size of approximately 30 randomized participants was determined outside of statistical considerations and is considered sufficient to address the primary research objectives.

10.3. Populations for Analyses

The following analysis populations are defined for this study.

Population	Description
Screened	All participants who signed the ICF
ITT	All randomized participants
Safety	All randomized participants who took ≥ 1 dose of study drug
PK	All randomized participants with ≥ 1 evaluable postdose PK assessment
PD evaluable	All randomized participants who completed the baseline and EoT visit assessments, had $\geq 80\%$ compliance with study drug dosing, and did not have any major protocol deviations that could affect the PD assessments

EoT=end of treatment; ICF=informed consent form; ITT=intent-to-treat; PD=pharmacodynamic(s); PK=pharmacokinetic(s)

10.3.1. Determination of PD Evaluable Population

The PD evaluable population will be identified and documented based on a review of protocol deviations before database lock by members of the study team, including but not limited to the medical monitor and study biostatistician. The categories of major protocol deviations to be reviewed include, but are not limited to, participants who:

- Did not meet key inclusion/exclusion criteria
- Received disallowed concomitant medication that could meaningfully impact results
- Had treatment compliance rate $<80\%$

The number and percentage of participants excluded from the PD evaluable population will be summarized by type of deviation and by treatment arm.

10.4. Statistical Analyses

This section summarizes the planned statistical analyses of the endpoints listed in Section 5. A more detailed and technical description of these analyses will be included in the statistical analysis plan (SAP).

10.4.1. General Considerations

Continuous variables will be summarized using the number of participants, mean, SD, minimum, median, interquartile range, and maximum values. Categorical variables will be summarized using the frequency and percentage of participants in each category. Percentages will be based on the total number of participants with non-missing values. If there are missing values, the number missing will also be presented, but without a percentage. Data summaries will be presented by treatment group (placebo, CY6463). All available data will be included.

10.4.2. Primary Endpoint(s)

Corresponding with the primary objective of evaluating the safety and tolerability of CY6463, TEAE incidence (number and percentage of participants with TEAEs) will be reported for each

treatment group for the Safety population. A TEAE is defined as an AE that started on or after the administration of randomized study drug through the last day of the Follow-up period.

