6.1.1. Screening Period

The Screening period begins with the execution of the informed consent form (ICF) at the Screening visit. After signing the ICF, each participant's study eligibility will be assessed according to the study's [Inclusion Criteria](#) and [Exclusion Criteria](#) listed in Section 7.

After the Screening visit, participants who are eligible for enrollment must begin complying with the lifestyle restrictions detailed in Section 7.5. They will also begin completing their daily study diary (Section 9.9).

The end of the Screening period will coincide with the start of the Treatment period.

Collection of adverse events (AEs) will begin after the ICF is signed and will continue through the Follow-up period.

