8.2. Dose Modification in Individual Participants

For a participant who does not tolerate the 15-mg QD dose (ie, three 5-mg tablets) as evidenced by an associated AE, the participant's dose may be de-escalated to 10-mg QD dose (ie, two 5-mg tablets).

- The decision to de-escalate study drug will be made on a per-participant basis jointly by the investigator and the CRO-based medical monitor, in consultation with the sponsor's medical monitor as needed; the modification will be recorded in the source documents and eCRF.
- Initiation of the 10-mg QD dose should occur only after the AE(s) prompting the dose reduction has/have either resolved or improved sufficiently to be considered mild in severity or, if the AE is a worsening of a pre-existing condition, has returned to baseline status.

If the 10-mg QD dose is also not tolerated, the participant will be discontinued from study drug for the remainder of the Treatment period due to the AE. See Section [7.6](#) for additional study drug discontinuation criteria and procedures.

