9.10.1. Time Period, Frequency, and Reporting Information

AEs, AESIs, and SAEs will be recorded on the AE eCRF starting from the signing of the ICF until the Follow-up visit after the final study drug dose.

- SAEs will be reported within 24 hours of the investigator's first awareness of the event
- Nonserious AESIs will be reported within 5 business days of the investigator's first awareness of the event

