Principal investigators must maintain all documentation relating to the conduct of this study for a period of 2 years after the last marketing application approval of CY6463 or, if not approved, 2 years after discontinuance of its development. If it becomes necessary for the sponsor or a regulatory authority to review documentation relating to the study, the investigator will permit access to such records.

Publication Policy

All data generated in this study will be the property of the sponsor. An integrated clinical and statistical report will be prepared at the completion of the study.

Please refer to the study center clinical trial agreement for publication and disclosure information.

APPENDIX 2. ADVERSE EVENTS, AESIS, AND SAES: DEFINITIONS AND PROCEDURES FOR RECORDING AND EVALUATING

Definition of Terms

Adverse Event (AE)

Per ICH, AEs are defined as any untoward medical occurrence in a patient or clinical study participant administered a pharmaceutical product and which does not necessarily have a causal relationship with this treatment. An AE can therefore be any unfavorable and unintended sign (including an abnormal laboratory finding), symptom, or disease temporally associated with the use of a medicinal (investigational) product, whether or not related to the medicinal (investigational) product.

Events Meeting the AE Definition

Any abnormal laboratory test results (hematology, clinical chemistry, or urinalysis) or other safety assessments (eg, ECG, radiological scans, vital signs measurements), including those that worsen from baseline, that are considered clinically significant in the medical and scientific judgment of the investigator (ie, not related to progression of underlying disease)Exacerbation of a chronic or intermittent pre-existing condition including either an increase in frequency and/or intensity of the conditionNew conditions detected or diagnosed after study intervention administration even though it may have been present before the start of the studySigns, symptoms, or the clinical sequelae of a suspected intervention-intervention interactionSigns, symptoms, or the clinical sequelae of a suspected overdose of either study drug or a concomitant medication. Overdose per se will not be reported as an AE/SAE unless it is an intentional overdose taken with possible suicidal/self-harming intent; such overdoses should be reported regardless of sequelae.
Events NOT Meeting the AE Definition

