
Any clinically significant abnormal laboratory findings or other abnormal safety assessments that are associated with the underlying disease, unless judged by the investigator to be more severe than expected for the participant's conditionThe disease/disorder being studied or expected progression, signs, or symptoms of the disease/disorder being studied, unless more severe than expected for the participant's conditionMedical or surgical procedure (eg, endoscopy, appendectomy): the condition that leads to the procedure is the AESituations in which an untoward medical occurrence did not occur (social and/or convenience admission to a hospital)Anticipated day-to-day fluctuations of pre-existing disease(s) or condition(s) present or detected at the start of the study that do not worsen

Serious Adverse Event (SAE)

An SAE is an AE occurring during any study phase (ie, at baseline or during Treatment, washout, or Follow-up), and at any dose of study drug that fulfills 1 or more of the following:

- Results in death
- Is immediately life-threatening (The term “life-threatening” refers to an event in which the participant was at risk of death at the time of the event. It does not refer to an event that hypothetically might have caused death if it were more severe.)
- Requires inpatient hospitalization or prolongation of existing hospitalization
- Results in persistent or significant disability or incapacity: a substantial disruption of a person’s ability to conduct normal life functions
- Results in a congenital abnormality or birth defect
- Is an important medical event that may require medical intervention to prevent 1 of the outcomes listed above.

Adverse Events of Special Interest (AESIs)

Based on the mechanism of action of sGC and anticipated vasodilation effects and based on the fact that CY6463 is a CNS-penetrant stimulator of sGC, the sponsor will collect AESIs in a timely manner. The AESIs relate to symptomatic hypotensive events and/or tachycardia, dizziness, syncope, and TEAEs related to change of neurobehaviors (ie, suicidality or euphoria).

In addition, because the marketed sGC stimulator riociguat includes bleeding events as a warning and precaution on its prescribing information (14), bleeding events will also be considered AESIs for CY6463 in this study. The specific list of AESI terms will be provided in the safety management plan.

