An AESI classification means that although an event might be nonserious, it will nonetheless be reported to the sponsor by completing the AE eCRF and filling in the AESI box within 5 business days of the investigator’s first awareness of the AESI event.

Treatment-Emergent Adverse Event (TEAE)

A TEAE is defined as an AE that started on or after the administration of randomized study drug through the last day of the Follow-up period.

Recording of AEs and/or SAEs

When an AE/SAE occurs, it is the responsibility of the investigator to review all documentation (eg, hospital progress notes, laboratory reports, and diagnostics reports) related to the event. The investigator will then record all relevant information in the AE eCRF page.

- It is **not** acceptable for the investigator to send photocopies of the participant’s medical records in lieu of completion of the AE eCRF.
- There may be instances when copies of medical records for certain cases are requested by the Safety CRO. In this case, all participant identifiers, with the

exception of the participant number, will be redacted on the copies of the medical records before submission to the Safety CRO.

AE terms should be reported in standard medical terminology when possible. For each AE, the investigator will evaluate the event based on signs, symptoms, and/or other clinical information. Whenever possible, the diagnosis (not the individual signs/symptoms) will be documented as the AE/SAE. The investigator will complete the AE CRF in its entirety, including details regarding event onset (date and time), resolution (date and time), intensity, causality, action taken, serious outcome (if applicable), whether or not any medications were given in response to the event and whether or not the event caused the participant to discontinue the study.

Assessment of Intensity

Intensity will be assessed by the investigator according to the following scale:

- **Mild:** An event that is easily tolerated by the participant, causing minimal discomfort and not interfering with everyday activities
- **Moderate:** An event that causes discomfort sufficient to interfere with normal everyday activities
- **Severe:** An event that prevents normal everyday activities

It is important to distinguish between serious and severe AEs. Severity is a measure of intensity whereas seriousness is defined by the criteria of this Appendix. An AE of severe intensity may or may not be considered serious.

Relationship to Study Drug

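### The TEAE definition goes by start date only, so a Screening AE that is ongoing at Day 1 and worsens on study drug can be missed by the primary endpoint

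*Combined protocol and SAP*

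**What the plan says.** Section 10.4.2 reports the number and percentage of participants with TEAEs in each group of the Safety population and defines a TEAE as "an AE that started on or after the administration of randomized study drug through the last day of the Follow-up period". Appendix 2 gives the same rule: "A TEAE is defined as an AE that started on or after the administration of randomized study drug through the last day" of Follow-up. Section 5 lists TEAE incidence as the only primary endpoint.

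AE recording begins well before dosing. Section 6.1.1 states: "Collection of adverse events (AEs) will begin after the ICF is signed and will continue through the Follow-up period". Section 9.10.1 sets the same window for the form, with AESIs and SAEs included: such events "will be recorded on the AE eCRF starting from the signing of the ICF until the Follow-up visit after the final study drug dose". Table 1 places Screening between Day -60 and Day -4.

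The protocol does deal with worsening when it says what counts as an AE:

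- Appendix 2 includes exacerbation "of a chronic or intermittent pre-existing condition including either an increase in frequency and/or intensity".
- Appendix 2 excludes day-to-day fluctuations only for conditions "present or detected at the start of the study that do not worsen".
- Section 8.2 makes provision "if the AE is a worsening of a pre-existing condition".

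On recording, Appendix 2 asks for "details regarding event onset (date and time), resolution (date and time), intensity, causality, action taken" and some further items for each AE. It does not say what a site should do when the intensity of an AE already on the form increases. Section 10.4 leaves technical detail to a SAP; no separate SAP text was available for this review.

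**The concern.** A definition based on start date alone has no place for an event that was present before the first dose and became worse after it. Worsening of an existing symptom on drug is a form of intolerance, and tolerability is what the primary objective sets out to describe. If such an event keeps its predose onset, it is treated as a pretreatment AE, and Section 10.4.4 provides only a listing for those.

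A nonserious event outside the AESI categories could therefore go from mild to severe on drug, or lead to stopping drug, and appear in no TEAE output. In a descriptive study with about 15 participants per arm, single rows of the safety tables carry much of the message.

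**Working it through.** The plan gives no figure to reproduce: Section 10.2 sets the sample size without statistical considerations, and Section 10.1 plans no test of the primary objective. The check is mainly of the text, with a short calculation for scale.

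**Step 1: can a predose AE be ongoing at Day 1?** Yes. Recording starts at consent. Section 6.1.2 says there is no Day 0, so consent on Day -60 is 60 days before Day 1. Table 1 schedules CSF sampling at Screening, so procedure-related AEs in that window are possible.

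**Step 2: which worsening events meet the definition?**

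| Case | Onset on the form | TEAE? |
|---|---|---|
| Condition in medical history, exacerbates after first dose | After dose (the exacerbation is the AE) | Yes |
| Screening AE, unchanged through Day 1 and after | Before dose | No, rightly |
| Screening AE, continuous through Day 1, worsens, entered as a new AE | After dose | Yes |
| Screening AE, continuous through Day 1, worsens, original entry updated | Before dose | No |

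Only the last row is a gap. No passage tells sites which of the last two rows to follow. Where the protocol describes later changes to a report, it describes updating: Section 9.10.1.1 has updated SAE information submitted on the AE eCRF, and Appendix 2 lets the investigator amend the causality entry. Updating the original entry is therefore a reasonable thing for a site to do.

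**Step 3: where would the event be missing?** From Section 10.4.4:

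- Missing from overall TEAE incidence (if the participant has no other TEAE); the tables by SOC and PT, severity and relationship; the summary of TEAEs leading to drug discontinuation; and the listings of TEAEs, severe TEAEs, drug-related TEAEs and TEAEs leading to study discontinuation.
- Still present in the pretreatment AE listing and, where applicable, the SAE summary and listing, the AESI listing and the listing of AEs leading to death. Neurobehavioral AESIs are an exception, because Appendix 2 itself words them as TEAEs.

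**Step 4: scale.** About 30 participants randomized 1:1 (Sections 6.2 and 6.3.1) gives 30/2 = 15 per arm.

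- One participant: 1/15 = 6.7 points. Two: 2/15 = 13.3. Three: 3/15 = 20.0.
- Exact (Clopper-Pearson) 95% interval for 0/15: the upper limit is 1 − 0.025^(1/15) = 21.8%, so 0 to 21.8%.
- For 1/15: the lower limit is 1 − 0.975^(1/15) = 0.17%, and the upper limit is 31.9%.

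**Step 5: how likely is at least one such participant?** The documents give no rate. Let q be an assumed proportion of participants with such an event. Then P(at least one of n) = 1 − (1 − q)^n.

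| Assumed q | n = 15 | n = 30 |
|---|---|---|
| 2% | 26.1% | 45.5% |
| 5% | 53.7% | 78.5% |
| 10% | 79.4% | 95.8% |
| 20% | 96.5% | 99.9% |

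These values show sensitivity to q and are not estimates for this trial.

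**The case against.** The strongest reply is that the protocol already makes a worsening an AE in its own right. If the AE is the exacerbation, it starts when the exacerbation starts, and a post-dose exacerbation meets the definition unchanged. Medical history is taken again on Day 1 (Table 1), and Section 8.7 separates prior from concomitant therapy at the start of study drug. Both fit a reading in which pre-existing means present at first dose, and on that reading a continuing Screening headache that worsens is a new AE. This is possible, and for conditions in the medical history the exacerbation clause settles the matter. But the documents nowhere state that pre-existing is judged at first dose, and they attach no new entry or onset date to a worsening.

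The second reply is that the effect is small and unproven. The analysis is descriptive, both arms have the same rule, overall incidence moves only for a participant with no other TEAE, and any single misclassified event is worth 6.7 points. The 0/15 and 1/15 intervals overlap heavily. Dose changes and action taken reach the eCRF, and laboratory, vital sign and ECG changes are summarized whatever the AE onset. All of this stands and limits the weight of the point. It does not put the event back into the tolerability tables.

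The third reply is that a recording note alone would close the gap, and that also widening the definition could flag one event twice. If the original entry keeps its predose intensity and the worsening has its own entry, only the second qualifies; incidence is counted per participant in any case.

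**Conclusion.** The concern holds in its conditional form. Under the written rule, an AE first recorded in Screening, continuous through Day 1, that worsens on drug and stays under its original entry is not a TEAE. It is left out of every output restricted to TEAEs, and out of the primary count if the participant has no other TEAE.

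The effect is 6.7 points per affected participant, assuming 15 per arm; a PT row or the drug-discontinuation row with no other case goes from 0% (exact 95% interval 0 to 21.8%) to 6.7% (0.2 to 31.9%). How many participants would be affected cannot be derived from the documents. The expected effect is undercounting; a distorted comparison would need worsening to differ by arm, which is not shown.

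The conclusion assumes that neither the SAP nor the eCRF instructions contain a rule on worsening. It is a change that should be made, not a fatal flaw.

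**What to change.** In Section 10.4.2 and Appendix 2, define a TEAE as an AE that begins on or after the first dose of study drug, or that began earlier and increases in intensity or becomes serious on or after that dose, up to the end of Follow-up. Use the same wording in the SAP.

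In the CRF completion instructions, have sites enter such a worsening as a new AE with its own onset date and leave the predose intensity on the original entry. This must reach sites prospectively: if intensity is overwritten on one entry, the date of worsening may not be recoverable, and a SAP rule alone could not repair that.

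The cost is one sentence in two places and a CRF note. The downside is some additional AE entries and possibly a slightly higher reported TEAE rate. No visit, procedure or treatment rule changes.
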